### Serious Adverse Event Definition/Qualification

A SAE is defined as an AE that results in any of the following outcomes:

- Death (note that death is the outcome of a SAE and the cause of death should be listed as the AE),
- Life-threatening event,
- In-patient hospitalization or prolongation of existing hospitalization,
- A persistent or significant disability/incapacity,
- Congenital anomaly or birth defect,
- Any other important medical event that may not result in death, be life-threatening, or require
  hospitalization, may be considered a SAE when, based upon appropriate medical judgment, the
  event may jeopardize the participant and may require medical or surgical intervention to prevent
  one of the outcomes listed above.

In the event of a SAE, the participant may be dropped from the study if the Investigator deems it necessary.

#### **Serious Adverse Event Reporting Instructions**

If in the opinion of the Investigator the event meets the criteria of a SAE the following procedures will be followed:

- The Investigator will notify Institutional Review Board (IRB) of the SAE within the parameters and timeframe specified under the IRB Standard Operating Procedures (SOP). An initial report followed promptly by a complete report will be forwarded to the IRB, when applicable.
- If a participant is hospitalized or hospitalization is prolonged due to the SAE, the hospital discharge summary will be obtained if possible.

- If a death occurs and an autopsy is performed, a copy of the autopsy report will be obtained if possible.
- All efforts must be undertaken to obtain follow-up information promptly.

### **Recording of Adverse Events**

All AEs (AE or SAE) will be recorded on the AE study documents. For participants who have an ongoing AE at their final study visit, follow-up information will be captured in the AE eCRF page which will be completed after 30 days.

#### **Serious Adverse Event Follow-Up**

For all ongoing SAEs occurring during the study, the Investigator must submit follow-up reports regarding the participant's subsequent course. All SAEs that are ongoing at the end of the study or upon discontinuation of the participant's participation must be followed until either:

- The event resolves, or
- The event/condition has stabilized (e.g., in the case of persistent impairment), or
- The event returns to baseline, if a baseline value is available, or
- The participant dies, or
- The event can be attributed to other than the study beverage, or to other than the study conduct.

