#### Relationship

The Investigator will also judge the likelihood that the AE was related to the study beverage and document this on the appropriate study documents as:

NOT RELATED	This category applies to those adverse experiences which, after careful consideration, are clearly and incontrovertibly due to extraneous causes (disease, environment, etc.).
UNLIKELY	In general, this category can be considered applicable to those experiences that after careful medical consideration at the time they are evaluated, are judged to be, unlikely related to the study beverage.

POSSIBLY	This category applies to those adverse experiences for which, after careful medical consideration at the time they are evaluated, a connection with the study beverage administration appears possible but cannot be ruled out with certainty.
PROBABLY	This category applies to those adverse experiences that, after careful medical consideration at the time they are evaluated, are felt with a high degree of certainty to be related to the study beverage.
DEFINITELY	This category applies to those adverse experiences which, the Investigator feels are incontrovertibly related to the study beverage.

Appropriate therapeutic action and follow-up measures will be performed by the Investigator in accordance with appropriate medical practice standard of care.

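### For SAEs still open at study end or discontinuation, the causality exit is joined by an 'or' and names a beverage the trial does not test, so procedure-caused and even diet-caused events can leave follow-up before their final outcome is known

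*Protocol*

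**What the plan says.** Three sections of the protocol bear on this point.

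**Serious Adverse Event Follow-Up** has two separate rules. The first covers the study period and has no causality exit: "For all ongoing SAEs occurring during the study, the Investigator must submit follow-up reports". The second covers "All SAEs that are ongoing at the end of the study or upon discontinuation" and requires follow-up until one of five conditions is met. Four describe the event's course: resolution, stabilisation, return to baseline, or death. The fifth is "The event can be attributed to other than the study beverage, or to other than the study conduct".

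**Recording of Adverse Events** applies whatever the cause: "All AEs (AE or SAE) will be recorded on the AE study documents". It adds: "For participants who have an ongoing AE at their final study visit, follow-up information will be captured in the AE eCRF page". That record is due once, at 30 days.

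**Relationship** gives a five-level causality scale, from not related to definitely related. Each event is judged against a study beverage. The lowest level is reserved for events "clearly and incontrovertibly due to extraneous causes".

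The Study Synopsis, Research Strategy and Description of Ketogenic Diet make the intervention a 52-week ketogenic diet. Broth and electrolyte packs are supplied to offset sodium loss, but no beverage is described as the intervention under test.

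**The concern.** The fifth condition ends follow-up on an opinion about cause, where the other four end it on what happened to the participant. Such an exit is workable if it releases only events unrelated to the trial. As worded it releases more than that, for three reasons:

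- The limbs are alternatives, so an event need only fall outside one of them.
- One limb refers to a product that is not the intervention.
- No causality grade is named as the threshold for release.

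At stake is the completeness of late safety outcomes. The clause also operates at discontinuation. Under Early Termination, the SAE definition section and Withdrawal of Participants, a marked creatinine rise, an SAE or another adverse event may lead to a participant leaving. How such an event evolves afterwards helps to judge whether the diet caused it. In a single-arm study there is no control group against which to check the investigator's attribution.

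**Working it through.** No arithmetic applies. The protocol gives no figure linked to this rule, so the check applies the wording to each possible cause and then to each stage of follow-up.

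**Step 1. Which events meet the exit?** Limb 1 is 'other than the study beverage'; limb 2 is 'other than the study conduct'. Under 'or', meeting either limb releases the event.

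| Cause of the SAE | Limb 1 as written | Limb 2 | Released as written? |
|---|---|---|---|
| Study procedure (e.g. an imaging visit) | met | not met | yes |
| Ketogenic diet | met literally, since the diet is not a beverage | met only if the diet is not counted as study conduct | yes |
| Unrelated illness | met | met | yes |

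Only the third row is a release that a reasonable drafter would want.

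**Step 2. Does one edit repair it?**

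- *Correct the noun only (beverage becomes diet), keep 'or'.* A procedure-caused SAE is still other than the diet and is still released. A diet-caused SAE is released only if the diet is not counted as study conduct.
- *Change 'or' to 'and' only, keep 'beverage'.* A procedure-caused SAE is no longer released. A diet-caused SAE still meets limb 1, so its release depends on whether the diet counts as study conduct.
- *Make both edits.* Procedure-caused and diet-caused events stay in follow-up. Only events unrelated to both are released.

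Both edits are therefore needed.

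**Step 3. Is the exit tied to the causality scale?** The follow-up section asks only that the event can be attributed elsewhere and cites no grade. The scale's lowest grade demands "clearly and incontrovertibly due to extraneous causes". Nothing in the follow-up section says that this standard applies. The scale also assesses relation to the beverage alone, so relation to study conduct has no grading.

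**Step 4. What information is exposed?**

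| Stage | Rule | Causality exit? |
|---|---|---|
| During the study | SAE recorded; follow-up reports mandatory | no |
| Ongoing at the final visit | eCRF follow-up page completed after 30 days | no |
| Still unresolved after that record | five-condition list | yes |
| Discontinued without a final visit | five-condition list; application of the 30-day page unclear | yes |

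Only the last two rows are exposed, and what is exposed is the final outcome, not the existence of the event.

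**The case against.** The strongest reply is that the clause sits among safeguards that do not depend on attribution. Every SAE is recorded. Reports are mandatory during the study. Events ongoing at the final visit get a 30-day record. The SAE reporting section asks for prompt follow-up information and the hospital discharge summary, and the withdrawal section asks that observations be completed as far as possible. The sponsor also very probably meant release for events unrelated to the study as a whole, and the diet can naturally be read as part of study conduct.

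Much of this stands, and it rules out several stronger readings that a reader might infer:

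- *That any ongoing SAE can be dropped, or that its outcome goes unrecorded.* The list governs only events open at study end or discontinuation, and the recording rules apply regardless of cause.
- *That the safety count is understated.* Ending follow-up removes no SAE from the tally. For the same reason, 5% (one event in 20) and 16.8% (the upper two-sided 95% bound for none in 20) describe incidence and do not measure the effect of this clause.
- *That an event graded POSSIBLY would be released.* That grade means a connection "appears possible but cannot be ruled out with certainty", which hardly supports attributing the event elsewhere.
- *That kidney events will usually be put down to the underlying disease.* This is plausible, but the protocol says nothing on how such events will be attributed.

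What the reply does not do is close the gap. The 30-day page is a single completion triggered by a final visit. The best-efforts sentences set no endpoint. The five-condition list is the specific rule on when follow-up stops, and none of the other provisions overrides it. Probable intent does not help the person applying the rule when the wording says something else.

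**Conclusion.** The point holds in a limited form. Followed as written, the fifth condition permits release of SAEs caused by study procedures and, on the literal noun, of SAEs caused by the diet. The loss is confined to the final outcome of SAEs unresolved after the 30-day record, or of those in participants who leave without a final visit. Neither the SAE count nor the analyses of kidney volume, GFR and albuminuria change.

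The number of events affected cannot be estimated, because the protocol gives no expected SAE or discontinuation rate. With 20 participants it may be none.

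The conclusion assumes that the five conditions are alternatives, as the text states, and that no study document outside this protocol defines the beverage or study conduct differently. The release of procedure-caused events does not depend on how the beverage wording is resolved. The release of diet-caused events does, and once the noun is corrected it depends on whether the diet counts as study conduct.

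**What to change.** Reword the fifth condition so that follow-up may end on causality only when the event is graded NOT RELATED to the ketogenic diet **and** NOT RELATED to the study procedures. In the Relationship section, replace the beverage with the ketogenic diet and have the investigator grade relation to study procedures as well, so that both halves of the condition have a grade behind them. The beverage wording in the opening Adverse Event Monitoring text and in Withdrawal of Participants should be corrected at the same time.

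Deleting the condition outright would also close the gap, but it is more debatable: it would require open-ended follow-up of events clearly unrelated to the trial. Restricting the exit is enough.

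The cost is a short protocol amendment, one additional causality field, and a few extra follow-up contacts among 20 participants. No visit, sample size or analysis changes.

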# Safety and Adverse Events via MRI

An adverse event is defined as illness, signs or symptoms that worsen over the course of the study. Abnormal lab tests, if deemed by the investigator to have resulted from ketogenic diet intervention, would be considered an adverse event. If the abnormal lab results lead to symptoms, further diagnostic tests, or withdrawal from the study, they are considered adverse events.

MRI at 0.55 Tesla, 1.5 Tesla, or 3 Tesla is considered a minimal risk procedure. There are no additional safety risks associated with the investigational MRI imaging. For patients receiving investigational 3 Tesla MRI (or lower field strength) imaging, the associated risks are the same as those that would normally be encountered in a standard of care MRI examination, and they are as follows:

Magnetic Resonance Imaging devices use three different types of electromagnetic fields that may pose potential risks to subjects undergoing MRI examinations. These are static magnetic fields, time varying magnetic field gradients, and radiofrequency (RF) electromagnetic fields.

- 1) Static magnetic fields exert forces on magnetic objects and induct electric currents in any conductive material, imposing two main risk categories:
  - a) Dislodgement or malfunction of medical implants or metallic foreign objects.
  - b) Current induction in tissue and subsequent alteration of physiologic function.

The FDA has classified MRI up to 8 Tesla as Non-Significant Risk.

In addition, subjects may be harmed by

- Loud noise from the MRI device.
- Some subjects may experience mild transient vertigo and/or metallic taste when they are being moved into the MRI system.
- Subjects may experience discomfort from the blood pressure cuff and finger clamp from the pulse-oximeter. Some subjects may experience feelings of being closed in if they are claustrophobic.
  - Long-term effects of high field MRI are not known at this time.

Risk from static, time varying magnetic field gradients and radiofrequency fields are at or below the FDA limits and thus risks are identical to standard field strength MRI units.

All above listed known effects of exposure to static magnetic fields, switched magnetic field gradients and RadioFrequency are transient, i.e. vertigo, spontaneous visual light perceptions, metallic taste, peripheral nerve stimulation as well as RF heating will end once exposure to the fields is ended. Based on this, cumulative effects are not expected, however long-term effects are not known at this time.

To minimize risks from the static magnetic field as with standard MRI, the following subjects will be excluded from this study (see MRI Safety Screening Forms for further details):

- Subjects who have any type of bioimplant activated by mechanical, electronic, or magnetic means (e.g., cochlear implants, pacemakers, neurostimulators, biostimulators, electronic infusion pumps, etc.).
- Subjects who have any type of ferromagnetic bioimplant that could potentially be displaced or damaged.
  - Subjects who have cerebral aneurysm clips.
- Subjects who may have shrapnel imbedded in their bodies (such as from war wounds), metal workers and machinists (potential for metallic fragments in or near the eyes), severe car accident victims.

Because effects of high field MRI are not known at this time also excluded are:

- Subjects who have permanent tattoo (e.g., eye liner) (may contain metallic coloring).

Also excluded are subjects incapable of giving informed written consent

- Subjects who cannot adhere to the experimental protocols for any reason, or have an inability to communicate with the researcher.
- Subjects who have limited mental ability to give informed consent, mentally retarded, altered mental status, mental disability, confusion, or psychiatric disorders.
  - Prisoners

To minimize discomfort we will also exclude subjects who exhibit noticeable anxiety and/or claustrophobia or who exhibit severe vertigo when they are moved into the MRI system.

All subjects will be given ear protection to prevent risks from loud noise.

#### CONDUCT OF THE STUDY

#### 1. Ethics and Regulatory Considerations

This study will be conducted according to Good Clinical Practice Guidelines, the Declaration of Helsinki (2004) and United State Code of Federal Regulation Title 21. Signed written informed consent for participation in the study will be obtained from all participants before protocol-specific procedures are carried out. Participants will be informed of their right to withdraw from the study at any time. Participants will be informed that their participation in the study is completely voluntary, personal information will be both coded with a study ID to preserve anonymity.

#### 2. Institutional Review Board

The Investigator will ensure that an appropriately constituted IRB, in compliance with the requirements of 21 CFR 56, reviews and approves the clinical study. Before the study is started, the Investigator will forward copies of the protocol and consent form for this study to the IRB for review and approval. IRB approval must refer to the study by exact protocol title and number, identify the documents reviewed, and state the date of review. The IRB must be informed of all subsequent protocol amendments. No alterations, modifications to IRB-approved documents, including the protocol, protocol summary, consent form, recruitment materials and questionnaires will be allowed. The IRB must also be informed of all SAEs and of unexpected AEs as outlined in the IRB's SOPs or reporting guidelines.

#### 3. Informed Consent and Protected Health Information

The study will be explained verbally as well as on the informed consent document. Each participant will be given ample opportunity to inquire about details of the study and to read and understand the consent form before signing it. It will be made clear that participants can withdraw from the study at any time.

Each participant's signed informed consent document must be kept on file by the Investigator. The participant should receive a copy of the informed consent document. A participant may not be admitted to the study unless informed consent of the participant (or his/her legally authorized representative) has been obtained.

#### 4. Participant Confidentiality

The Investigator is responsible for ensuring that participants' anonymity will be maintained. For all the data collected over the course of the study for each participant (i.e., records, biological samples and questionnaires) a unique subject identifier (i.e., a code) will be assigned and used instead of the subject's name. The code for each participant which links the subject name with their identifier will only be available to research personnel. Electronic CRFs or other documents will identify participants by initials, number, or code, and not by name. The Investigator will keep a separate log showing codes, names, and addresses. Any records that contain the subject's name and identifier will either be stored in the Kinesiology file storage room in a file cabinet (locked) or protected on a computer via password protection on the individual digital file and password protection on the computer the file(s) are stored on. All other records that contain the subject identifier only will also be kept in either a file cabinet in our locked file storage room or on a password protected computer. Subject names will never be used in any presentation or publication resulting

from this study. The records will be maintained until the data are published and up to a maximum of ten years after the completion of the study. All records or biological data obtained after signing of the informed consent (including the screening visit, even for subjects that are not eligible for participation in the study) are treated with the same confidentiality safety measures as those subjects who qualify. Any information obtained during the prescreening for participants that were not eligible will be deleted

### 5. Withdrawal of Participants from the Study

Participants may be removed from the study for any of the following reasons:

- A participant requests discontinuation;
- The Investigator initiates removal for medical or compliance reasons;
- Occurrence of any AE or condition that could, in the Investigator's opinion, interfere with the evaluation of the effect of the study beverage or put the participant at undue risk.

It is understood by all concerned that an excessive rate of withdrawals can render the study uninterpretable, therefore, unnecessary withdrawal of participants should be avoided. Should a participant decide to withdraw, all efforts will be made to complete and report observations as thoroughly as possible. In the event that a participant is withdrawn from the study, the reason for the withdrawal will be documented in the eCRF.

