#### **OUTCOMES**

**Study Endpoints:** Change in total kidney volume (TKV) from baseline to 1 year to assess disease progression. Change in albuminuria and GFR.

**Primary Objective:** The primary Objective will be to determine htTKV at baseline and 1 year after ketogenic diet intervention.

**Secondary Objectives:** The secondary endpoints will be measurement of GFR and 24-h urine microalbumin.

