# MRI Imaging protocol for htTKV:

Patients will undergo investigational Magnetic Resonance Imaging for assessment of Total Kidney Volume at baseline and 1 year of study participation. MRI specific safety screening will be performed by a qualified imaging team member prior to the imaging session. Patients will be prepared for imaging by the imaging team member and imaging will be completed over the abdominal area, imaging will last no more than one hour. Studies will be carried out using FDA approved 0.55T, 1.5T, or 3T MRI units. Imaging sequences will include 2D T2-weighted Turbo Spin Echo and 3D T1-weighted fat-water separated sequences. Intravenous contrast agent will not be administered. Images of the abdomen and kidneys will be analyzed in order to calculate height-adjusted TKV according to established practices of the Mayo Imaging Classification [1].

The presence of pre- and post-treatment MRI and laboratory tests for comparing kidney size is crucial for evaluating the effectiveness of the treatment. However, there is a potential for inter and intra-observer bias in the measurement of kidney size. To address this issue, several steps and strategies can be implemented:

**Standardized Protocols**: Develop standardized protocols for measuring kidney size that all observers must adhere to. These protocols should include specific guidelines for image acquisition, positioning of patients, and measurement techniques.

**Training and Calibration:** We have ensured that that all observers receive comprehensive training on the measurement techniques and protocols, prior to the study. This training includes both theoretical and hands-on components. Additionally, periodic calibration sessions can be organized to minimize observer variability.

Quality Control Checks: We will regularly monitor the quality and consistency of measurements throughout the study. If significant variability is observed, additional training and calibration sessions should be conducted.

Interpretation Guidelines: We have developed clear guidelines for interpreting the MRI and lab results. This can help standardize the assessment of improvement in kidney size, reducing the risk of bias in interpretation.

Documentation and Audit Trails: Maintain detailed documentation of all measurements, protocols, and observer assignments. This information can be audited to ensure compliance and identify any potential sources of bias.

Table 1 | Table of Study Procedures.

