#### DATA ANALYSIS AND STATISTICAL METHODS

The study will focus on percent change for TKV, albuminuria, and GFR pre and post the ketogenic dietary intervention. We will collect the following data for each patient including age, sex, race, baseline medications, BMI, albuminuria, GFR, and blood pressure. The univariate analysis will include the above variables and use analysis of variance to assess changes at baseline and at 12 months. Based on the univariate analysis, we will perform linear regression. Ketogenic diet administration will be forced into the model. Other variables will be chosen based on strength of the univariate analysis. Our outcome of interest will be percent change in TKV, albuminuria, and GFR. In regard to MR Imagining, we will utilize a statistical method to account for observer variability. Statistical techniques such as intra-class correlation coefficients (ICC) can quantify the level of agreement between different observers and help correct for any bias.

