# **Early Termination:**

We anticipate that participants will follow the diet plan as closely as possible to ensure the study's success. In the event of a more than twofold increase in serum creatinine, reaching Stage II acute kidney injury, we may consider early termination from the study. However, we recognize that individual differences, especially in creatinine levels related to protein intake, may occur. Therefore, decisions about early termination will be made in consultation with a physician. Subsequent visits will involve careful consideration of the rate of increase in serum creatinine, allowing the physician to determine whether continued participation is safe and advisable for the participant's health. Our top priority is the well-being of each participant, and any decisions about early termination will be made with their best interests in mind.

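### Participants can be removed from the study for poor compliance with no 12-month MRI required afterwards, so the kidney-volume result can become an estimate in adherent completers

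*Protocol*

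**What the plan says.** Section 5 of Conduct of the Study gives the grounds on which a participant may leave the study. The second is "The Investigator initiates removal for medical or compliance reasons". It gives no compliance criterion and does not distinguish stopping the diet from ending study participation.

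Two sentences then deal with what follows. For a participant's own decision: "Should a participant decide to withdraw, all efforts will be made to complete and report observations as thoroughly as possible". For one who is withdrawn: "In the event that a participant is withdrawn from the study, the reason for the withdrawal will be documented in the eCRF". Neither names the 12-month MRI. Serious Adverse Event Follow-Up and Recording of Adverse Events carry ongoing adverse events past the end of participation, but not kidney volume.

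On the outcome, the Outcomes section states: "The primary Objective will be to determine htTKV at baseline and 1 year after ketogenic diet intervention". The MRI section schedules imaging for "Total Kidney Volume at baseline and 1 year of study participation". Table 1, the visit list and Timing of Monitoring agree that MRI is done at baseline and month 12 only. Research Strategy also lists an MRI at 6 months, which conflicts with the other places and must be reconciled.

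On the analysis: "The study will focus on percent change for TKV, albuminuria, and GFR pre and post the ketogenic dietary intervention". The Synopsis describes an open-label, single-arm study of 20 patients.

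**The concern.** In a single-arm pre/post study the mean change among those measured is the whole result. There is no comparator arm in which selective loss would show up. If the least adherent participants leave before month 12 and are not scanned, the mean describes people who kept to the diet, not people who were started on it.

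There is reason to expect that removals would not be random. Adherence is assessed weekly by study staff, ketones are reported daily, and GFR is checked between baseline and month 12. The investigator, who can remove participants, also leads the monitoring. Supplied meals end at week 6, which leaves 46 weeks (52 − 6) of free-living diet in which lapses are foreseeable. A second, medical route under Early Termination ("we may consider early termination from the study") is tied to serum creatinine. It too may be related to disease course, although the documents do not quantify that.

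An analysis plan can define a population or a missing-data method, but it cannot recover a scan that was never taken. The point therefore belongs to the protocol.

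**Working it through.** **Is the primary outcome lost on removal?**

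1. The endpoint is change in kidney volume from baseline to 1 year (Outcomes).
2. Four places put the only post-baseline MRI at month 12 (MRI section, Table 1, visit list, Timing of Monitoring).
3. A participant removed earlier therefore has no post-baseline volume unless the site recalls them. If the 6-month scan in Research Strategy were carried out, it still would not supply the 1-year value.
4. No section asks for a recall after an investigator's removal.
5. One participant is 1/20 = 5% of the primary data.

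**How large could the bias be?** The protocol gives no expected growth, standard deviation, effect size or dropout rate, so there is no stated figure to reproduce. The values below are assumptions for illustration.

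Let f be the share removed, and let g_rem and g_ret be the annual percentage growth in removed and retained participants.

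- Mean over all who started = (1 − f) × g_ret + f × g_rem
- Overstatement by completers = that mean − g_ret = f × (g_rem − g_ret)

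With g_ret = 3%/yr and g_rem = 5%/yr (gap of 2 points):

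| Removed of 20 | f | Completer mean | Mean over all 20 | Overstatement (points/yr) |
|---|---|---|---|---|
| 2 | 0.10 | 3.0% | (18×3 + 2×5)/20 = 3.2% | 0.2 |
| 4 | 0.20 | 3.0% | (16×3 + 4×5)/20 = 3.4% | 0.4 |
| 6 | 0.30 | 3.0% | (14×3 + 6×5)/20 = 3.6% | 0.6 |
| 8 | 0.40 | 3.0% | (12×3 + 8×5)/20 = 3.8% | 0.8 |

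**Sensitivity to the gap**, over the same 10–40% removed:

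- gap 0: bias 0
- gap 1 point: 0.1 to 0.4
- gap 3 points: 0.3 to 1.2

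**If the diet has no effect.** A simulation of 20 participants removed 2, 4 or 6 of them on a score correlated with growth (assumed SD 3 or 5 points). With zero correlation the completer mean did not shift. With correlation 0.3 to 0.5 it was too low by 0.16 to 1.19 points. What matters is the link between removal and growth, whether it arises through a diet effect or in another way.

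**The case against.** The case on the other side has substance.

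- **Removal is permissive and discouraged.** Section 5 itself warns that too many withdrawals could make the study impossible to interpret and asks that needless ones be avoided. Under Objective and Subjective Markers, the response to ketosis deviations is counselling. This stands: the result can become a completers' estimate, but it need not. The text neither limits the compliance ground nor secures the MRI once it is used.
- **The contrast between the two sentences is partly inference.** The duty that "the reason for the withdrawal will be documented in the eCRF" may apply to every withdrawal, and it does not say that nothing else is collected. A reader might infer that the protocol tells sites not to scan removed participants. It does not; it is silent. The defect is that nothing requires the scan.
- **Compliance is undefined.** It may mean missed visits rather than diet. That ambiguity is part of the problem, but dietary non-adherence is a reading, not a certainty.
- **The direction is not guaranteed.** A reader might infer a sure bias in favour of the diet. That needs removed participants to grow faster than retained ones.
- **A larger effect is tempting.** With 30% removed and growing at 6%, the overall mean is 0.7×3 + 0.3×6 = 3.9%. Set against 5%/yr, that is a 22% reduction, where completers show 40%. This assumes non-adherers do worse than the 5% reference, for which no basis is given. The protocol also uses 5%/yr as a marker of rapid progression, not as a planned comparator.
- **Feasibility is not hidden.** Reasons for withdrawal are recorded and adherence is tracked, so poor feasibility would remain visible.
- **Analysis sets may be in an SAP.** Their absence from the protocol is not part of this point.

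**Conclusion.** The point holds in a limited form. The protocol permits removal from the study for compliance and does not require the 12-month outcome afterwards. In a 20-person single-arm study, each use of that rule can cost 5% of the primary data, selectively by adherence.

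Under the assumed 10–40% removed and a growth gap of 2 points/yr, the overstatement is 0.2 to 0.8 points/yr. It scales with the gap and is zero if removal is unrelated to growth. The removal rate, both growth rates and the reading of compliance as dietary adherence are assumptions. The missing follow-up requirement is not; it follows from the text. The change is worth making because it is cheap and must be in place before participants reach month 12.

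**What to change.** In section 5:

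- Separate stopping the diet from leaving the study, and state that non-compliance with the diet alone does not end follow-up.
- Seek the scheduled 12-month MRI and laboratory tests from every participant who started the diet, whoever initiated the stop, unless consent is withdrawn or the assessment is medically unsafe.
- Include these participants in the main pre/post estimate. Detailed definitions of analysis sets can be left to the SAP.

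Medical stopping rules are unchanged. Separately, reconcile the 6-month MRI in Research Strategy with the MRI section, Table 1, the visit list and Timing of Monitoring.

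The cost is a short amendment and some retention effort. The month-12 assessments are already planned for all 20 participants. The headline estimate may look less favourable than one from completers.
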